**Table 7 - Cetuximab Infusion-related reaction dose modification and treatment guidelines**

| NCI CTCAE Grade   | Dose modification  |
|--|---|
| Grade 1
Mild reaction; infusion interruption not indicated; intervention not indicated   | Decrease the cetuximab infusion rate by 50% and monitor closely for any worsening.  |
| Grade 2
Therapy or infusion interruption indicated but responds promptly to symptomatic treatment (eg, antihistamines, NSAIDs, narcotics, IV fluids); prophylactic medications indicated for ≤24 hrs.  | Stop cetuximab infusion and administer bronchodilators, oxygen, etc. as medically indicated.
Resume infusion at 50% of previous rate once allergic/hypersensitivity reaction has resolved or decreased to Grade 1 in severity, and monitor closely for any worsening                                       |
| Grades 3 or 4
Grade 3:
Prolonged (ie, not rapidly responsive to symptomatic medication and/or brief interruption of infusion); recurrence of symptoms following initial improvement; hospitalization indicated for other clinical sequelae (eg, renal impairment, pulmonary infiltrates) | Stop the cetuximab infusion immediately, administer epinephrine, bronchodilators, antihistamines, glucocorticoids, intravenous fluids, vasopressor agents, oxygen, etc, as medically indicated.
Permanently discontinue Cetuximab. The participant can continue treatment with pembrolizumab or SAR444245. |
| Grade 4:
Life-threatening; urgent intervention indicated   |   |

Abbreviations: CTCAE = Common terminology criteria for adverse events; IRR = Infusion related reaction; NCI = National Cancer Institute.

Guidelines for the management of SAR444245 IRR events are provided in [Table 8](#). Participants who develop Grade 2 IRR should have the next SAR444245 infusion given at half the infusion rate. For instructions on premedication at subsequent dosing, please see Section 6.1.2.1 of the master protocol.

**Table 8 - SAR444245 Infusion-related reaction dose modification and treatment guidelines**

| NCI CTCAE Grade   | Treatment   |
|---|---|
| 
Grade 1
Mild reaction; infusion interruption not indicated; intervention not indicated
  | 
If IRR happens during infusion, continuation of SAR444245a infusion is per Investigator's judgment following close direct monitoring of the participant's clinical status.
 
SAR444245 infusion may be interrupted at any time if deemed necessary.
 
If interrupted, IRR will be classified as Grade 2 as per NCI-CTCAE definition.
 
If IRR happens after completion of infusion, increase monitoring of vital signs as medically indicated until the participant is deemed medically stable in the opinion of the investigator.
   |
| 
Grade 2
Therapy or infusion interruption indicated but responds promptly to symptomatic treatment (eg, antihistamines, NSAIDs, narcotics, IV fluids); prophylactic medications indicated for ≤24 hrs.
                       | 
Interrupt SAR444245 infusion.
 
If symptoms resolve within 1 hour of interrupting drug infusion, the infusion may be restarted at 50% of the original infusion rate. Otherwise, dosing will be held until symptoms resolve and the participant will be premedicated for the next scheduled dose according to Section 6.1.2.1 of the master protocol.
 
Give the next infusion at half the infusion rate.
 
During or after completion of infusion, additional appropriate medical therapy may include but not limited to IV fluids, antihistamines, NSAIDs, acetaminophen, narcotics.
 
Increase monitoring of vital signs will be as medically indicated until the participant recovers.
 |
| 
Grade 3
Prolonged (ie, not rapidly responsive to symptomatic medication and/or brief interruption of infusion); recurrence of symptoms following initial improvement; hospitalization indicated for other clinical sequelae
 | 
Permanently discontinue SAR444245. The participant can continue treatment with the other anti-cancer therapy in combination.
 
During or after completion of infusion, additional appropriate medical therapy may include but is not limited to epinephrineb, IV fluids, antihistamines, NSAIDs, acetaminophen, narcotics, oxygen, vasopressors, corticosteroids.
 
Increase monitoring of vital signs as medically indicated until the participant recovers.
  |
| 
Grade 4
Life-threatening; urgent intervention indicated
   | 
Permanently discontinue SAR444245. The participant can continue treatment with the other anti-cancer therapy in combination.
 
During or after completion of infusion, additional appropriate medical therapy may include but is not limited to epinephrineb, IV fluids, antihistamines, NSAIDs, acetaminophen, narcotics, oxygen, vasopressors, corticosteroids.
 
Increase monitoring of vital signs as medically indicated until the participant recovers.
  |

a Information for preparation and storage of SAR444245 is provided in the pharmacy manual.

b In cases of anaphylaxis, epinephrine should be used immediately

Abbreviations: CTCAE = Common terminology criteria for adverse events; IRR = Infusion-related reaction; NCI = National Cancer Institute; NSAIDs: nonsteroidal anti-inflammatory drugs.

### 6.5.4.2 Anaphylaxis

Anaphylaxis should lead to immediate interruption of ongoing infusion, and to permanent discontinuation of pembrolizumab and cetuximab being administered.

Management should be prompt and may include but is not limited to administration of epinephrine, IV fluids, antihistamines, oxygen, vasopressors, corticosteroids, as well as increased monitoring of vital signs as medically indicated, until the participant recovers (see guidelines in (14, 31, 32)).

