#### 6.1.1 Investigational medicinal product

Investigational medicinal product (IMP) is defined as SAR444245, cetuximab and pembrolizumab administered as described in [Section 4.1](#). Details of each IMP component to be administered are shown in [Table 4](#).

Preparation and administration of IMP are detailed in the pharmacy manual. Hydration is required for SAR444245 infusions. Details are provided in Section 6.1.3 of the master protocol.

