#### 6.5.4.2 Anaphylaxis

Anaphylaxis should lead to immediate interruption of ongoing infusion, and to permanent discontinuation of SAR444245 being administered.

Management should be prompt and may include but is not limited to administration of epinephrine, IV fluids, antihistamines, oxygen, vasopressors, corticosteroids, as well as increased monitoring of vital signs as medically indicated, until the participant recovers (see guidelines) (24, 25, 26).

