#### 6.5.4.2 Anaphylaxis

Anaphylaxis should lead to immediate interruption of ongoing infusion, and to permanent discontinuation of SAR444245 and cetuximab being administered.

Management should be prompt and may include but is not limited to administration of epinephrine, IV fluids, antihistamines, oxygen, vasopressors, corticosteroids, as well as increased monitoring of vital signs as medically indicated, until the participant recovers (see guidelines in [5, 6, 7]).

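### The anaphylaxis sections of Cohorts A2 and B1 each leave out one study drug and do not agree with the infusion-reaction guidance in the same substudy

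*Protocol*

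**What the plan says.** **Cohort A2.** Section 6.1.1 opens with "Investigational medicinal product (IMP) is defined as SAR444245, cetuximab and pembrolizumab administered as described in" Section 4.1, so there are three study drugs. Section 6.5.4.2 reads: "Anaphylaxis should lead to immediate interruption of ongoing infusion, and to permanent discontinuation of pembrolizumab and cetuximab being administered". The infusion-reaction guidance in Section 6.5.4.1 gives a separate instruction for each drug:

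- Table 8 (SAR444245), Grades 3 and 4: "Permanently discontinue SAR444245. The participant can continue treatment with the other anti-cancer therapy in combination". A footnote attached to those rows adds: "In cases of anaphylaxis, epinephrine should be used immediately".
- Table 7 (cetuximab), Grades 3 or 4: "Permanently discontinue Cetuximab. The participant can continue treatment with pembrolizumab or SAR444245". The text before the table counts anaphylactic reactions among the severe cetuximab reactions.
- Table 6 (pembrolizumab), Grades 3 or 4, with its own note on anaphylaxis: the participant permanently leaves further study drug treatment.

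**Cohort B1.** The study drugs are SAR444245 and pembrolizumab (Section 6.1.1). Section 6.5.4.2 calls for "permanent discontinuation of SAR444245 being administered" and does not mention pembrolizumab. Section 6.5.4.1 states that pembrolizumab may cause anaphylaxis, and says that after a pembrolizumab reaction SAR444245 is delayed and may be given once symptoms resolve. Table 2 ends further study drug treatment after a Grade 3 or 4 pembrolizumab reaction. Table 3 stops SAR444245 after a Grade 3 or 4 reaction to it. Section 6.5.1 requires pembrolizumab to stop when toxicity stops SAR444245, with an exception.

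**Cohort B2.** The same sentence requires "permanent discontinuation of SAR444245 and cetuximab being administered", which is both of that cohort's drugs.

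**The concern.** The three substudies share one template sentence for anaphylaxis. In B2 it lists every study drug. In A2 it lists two of three, and the missing one is the investigational agent. In B1 it lists one of two. That pattern looks like a drafting slip rather than a deliberate rule.

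At stake is a life-threatening event for which a site can find two passages in the same substudy that differ on which drug is permanently stopped. Two sites could follow the protocol and keep different drugs going after the same event.

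**Working it through.** No arithmetic applies. The check takes each drug as the trigger and sets the passages side by side. It assumes that anaphylaxis falls in the Grade 3 or 4 rows of the infusion-reaction tables, which is where their anaphylaxis notes are attached.

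1. **A2, anaphylaxis on SAR444245.** Section 6.5.4.2, read literally, stops pembrolizumab and cetuximab and says nothing about SAR444245. Table 8 stops SAR444245 and lets the other therapy continue. The two instructions are opposed. If the section's closing words limit it to the drug then infusing, it gives no discontinuation rule here and only Table 8 does.

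2. **A2, anaphylaxis on cetuximab.** Both passages stop cetuximab. Section 6.5.4.2, read literally, also stops pembrolizumab. Table 7 says "The participant can continue treatment with pembrolizumab or SAR444245". This is a conflict on the literal reading, and none if only the infusing drug is meant.

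3. **A2, anaphylaxis on pembrolizumab.** Table 6 ends further study drug treatment. Section 6.5.4.2 does not name SAR444245. The passages differ if study drug in Table 6 means all three drugs.

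4. **B1, anaphylaxis on pembrolizumab.** Section 6.5.4.2 names only SAR444245, so it has no rule for the drug that caused the event. Table 2 ends further study drug treatment. Section 6.5.4.1, in a sentence with no grade limit, allows SAR444245 after symptoms resolve. Table 2 and Section 6.5.4.1 conflict if study drug covers both agents. Section 6.5.4.2, read literally, also conflicts with Section 6.5.4.1 because it stops SAR444245 permanently.

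5. **B1, anaphylaxis on SAR444245.** Section 6.5.4.2 and Table 3 agree that SAR444245 stops. Table 3 lets the other drug continue. Section 6.5.1 makes pembrolizumab stop too, unless the event is clearly attributable to SAR444245 alone and the participant has clinical benefit. These can be read together, but Section 6.5.4.2 does not point to either.

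The general rules do not clearly settle the matter. In A2, Section 6.5.1 lets the remaining component continue after one is stopped, which fits Tables 7 and 8 rather than the literal Section 6.5.4.2. The instruction in A2 and B1 to follow the most conservative recommendation is written for a participant with several toxicities, not for one event covered by two passages.

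**The case against.** The best defence rests on the closing words of the sentence. If it stops only the drug being infused at the time, cetuximab anaphylaxis stops cetuximab under both Section 6.5.4.2 and Table 7. SAR444245 anaphylaxis in A2 is then a gap that Table 8 fills. The passages also agree on acute care: the infusion is interrupted and epinephrine and supportive treatment are available. The tables are permissive about continuing other drugs, and Section 6.5.3 leaves the final dose-modification decision to the investigator. The master protocol, not shown here, may hold a common rule.

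Part of this stands. The Table 7 conflict depends on the reading and should be stated that way. The omissions survive either reading: the sentence still has no rule for SAR444245 in A2 or for pembrolizumab in B1. As to the master protocol, these sections state their own rule and do not refer to it.

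Three stronger inferences are tempting, and the documents do not support them:

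- That the sections name the wrong drugs. Nothing in the documents settles which drugs should stop, so the lists can only be called incomplete and inconsistent.
- That B1 contradicts its SAR444245 table. It does not. Section 6.5.4.2 and Table 3 agree, and the B1 tension lies on the pembrolizumab side.
- That the 2.2% rate of Grade 3 and 4 cetuximab infusion reactions in Section 2.3.1.2 sizes the problem, or that the response rate is distorted. That rate covers all such reactions, not anaphylaxis, and no passage links this wording to the response analysis.

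**Conclusion.** The point holds as an inconsistency in safety instructions. In A2, Section 6.5.4.2 omits SAR444245 and, read literally, runs opposite to Table 8. It also conflicts with Table 7 unless only the infusing drug is meant. In B1, Section 6.5.4.2 omits pembrolizumab despite recognised pembrolizumab anaphylaxis, and Table 2 and Section 6.5.4.1 differ on SAR444245 afterwards if study drug covers both agents.

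The frequency of anaphylaxis in these cohorts cannot be derived from the documents, so no event count is attached. Sample size, power and the response-rate figures are untouched. The case for correction rests on the seriousness of the event and the low cost of the change. It is worth making at the next amendment.

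**What to change.** In A2, reconcile Section 6.5.4.2 with Tables 6, 7 and 8. In B1, reconcile Section 6.5.4.2 with Tables 2 and 3, the discontinuation rule in Section 6.5.1, and the sentence in Section 6.5.4.1 on giving SAR444245 after a pembrolizumab reaction. For anaphylaxis on each study drug there should be one instruction stating what happens to every study drug in that cohort. The text should also make clear whether the sentence applies only to the drug then infusing, and what study drug means in the pembrolizumab tables. The sponsor's clinical team decides the content.

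The cost is wording in two substudies. No design or analysis element changes.

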### **6.5.4.3 Fever, flu-like symptoms and cytokine-release syndrome (CRS)**

Fever can frequently happen with infusion of IL-2 and may possibly evolve into flu-like symptoms or could be an early manifestation of CRS. Fever or flu-like symptoms should be graded according to CTCAE V5.0 and managed according to institutional standards.

Monitoring of vital signs is detailed in Safety Assessments ([Section 8.2.2](#)).

Cetuximab may be associated with CRS. Cytokine-release syndrome typically occurs within one hour after infusion and is less commonly associated with bronchospasm and urticaria. Cytokine-release syndrome is normally most severe in relation to the first infusion of cetuximab. Cetuximab related IRRs, including CRS, are discussed in [Section 6.5.4.1](#) of the protocol. Please refer to [Table 7](#) for Cetuximab IRR dose modifications and treatment guidelines.

Cytokine-release syndrome should be graded as per American Society for Transplantation and Cellular Therapy (ASTCT) criteria integrated with central laboratory cytokine results, and managed per guidelines in [Table 9](#). If any grade of CRS is suspected, sites should make every effort to draw an additional blood sample for cytokines levels (by central laboratory) prior to the administration of tocilizumab or alternative therapies per site practice in CRS management, as well as C-reactive protein (CRP) and ferritin (by local laboratory).

Sites should have at least 2 full doses of tocilizumab or alternative therapies per site practice in CRS management available and access to an intensive care unit (ICU), in case participants develop CRS.

Guidelines for management of CRS according to severity grading are provided in [Table 9](#). ASTCT CRS consensus grading scale is provided in Section 10.13 of the master protocol.

**Table 9 - Guidelines for the management of suspected cytokine release syndrome (CRS)**

| Event severity (ASTCT CRS Consensus Grading)   | Recommended SAR444245 dose modification and supportive care guidelines   | Recommended Cetuximab dose modifications and supportive care guidelines  |
|--|--|--|
| 
Grade 1
 
 
• Fever (Temperature <math>\geq 38^{\circ}\text{C}</math>)b
 
• No hypotension
 
• No hypoxia
 
  | 
No dose modification of SAR444245a
 
Appropriate symptomatic treatment may include but is not limited to IV fluids (care should be taken to not excessively hydrate if evidence of vascular leak), antihistamines, NSAIDs and acetaminophen.
 
Close direct monitoring of the participant's clinical status. Clinical and laboratory monitoring should initially be performed daily, then less frequently as the participant improves.
  | 
Decrease the cetuximab infusion rate by 50% and monitor closely for any worsening.
   |
| 
Grade 2
 
 
• Feverb (Temperature <math>\geq 38^{\circ}\text{C}</math>)
 
• Hypotension not requiring vasopressors
 
• and/orc hypoxia requiring low-flow nasal cannulad or blow-by.
 
 | 
Temporarily interrupt SAR444245 if event occurs during infusion
 
Additional appropriate medical therapy may include but is not limited to IV fluids (care should be taken to not excessively hydrate if evidence of vascular leak), antihistamines, NSAIDs and acetaminophen.
 
Increase monitoring of vital signs, cardiac and other organ functions closely as medically indicated until the participant recovers. Transfer to ICU may be required.
 
For participants with comorbidities, older age, or with oxygen requirement, hypotension, or participants in whom symptoms (eg, high grade fever) that do not respond to antipyretics within 72 hours treatment with corticosteroids and/or tocilizumab or alternative therapies per site practice in CRS management should be considered, as per guidance for Grade 3 events.
 
IMP may be resumed when clinical symptoms have resolved or improved to Grade 1 and corticosteroid taper. No dose modification is required but decreasing to half the infusion rate can be considered.
 | 
Stop cetuximab infusion and administer intravenous fluids, bronchodilators, oxygen, etc. as medically indicated. Resume infusion at 50% of previous rate once the event has resolved or decreased to Grade 1 in severity, and monitor closely for any worsening.
 |

| Event severity (ASTCT CRS Consensus Grading)  | Recommended SAR444245 dose modification and supportive care guidelines  | Recommended Cetuximab dose modifications and supportive care guidelines   |
|---|---|---|
| 
Grade 3
 
 
Feverb (Temperature <math>\geq 38^{\circ}\text{C}</math>)
 
Hypotension requiring a vasopressor with or without vasopressin
 
And/orc hypoxia requiring high-flow nasal cannulad, face mask, nonrebreather mask, or Venturi mask
 
  | 
If CRS grade 3, temporarily cycle delay SAR444245, and resume subsequent treatment only when symptoms have resolved or improved to Grade 1.
 
SAR444245 can be either restarted at ■ <math>\mu\text{g}/\text{kg}</math> or permanently discontinued, as clinically indicated.
  | 
Stop the cetuximab infusion immediately, administer epinephrine, bronchodilators, antihistamines, glucocorticoids, intravenous fluids, vasopressor agents, oxygen, etc., as medically indicated. Cetuximab should be permanently discontinued. The participant can continue treatment with SAR444245.
 |
| 
Grade 4
 
Life-threatening consequences; urgent intervention indicated
 
 
Feverb (Temperature <math>\geq 38^{\circ}\text{C}</math>)
 
Hypotension requiring multiple vasopressors (excluding vasopressin)
 
And/orc hypoxia requiring positive pressure (eg, CPAP, BiPAP, intubation and mechanical ventilation)
 
 | 
If CRS Grade 4, permanently discontinue SAR444245.
 
If CRS Grade 3 or Grade 4, initiate IV corticosteroids (outside of the context of CAR-T cells, corticosteroids alone maybe initiated in first intention) and tocilizumab or alternative therapies per site practice in CRS management considered, and/or epinephrine and/or other vasopressors should be administered as needed. Participants with severe CRS may require management in intensive care setting, with monitoring of clinical status and laboratory tests performed at least daily.
 
As the participant improves, the intensity of the monitoring and setting can be decreased, but the participant should not be discharged from the hospital until clinically stable. Corticosteroids can then be administered IV or orally every 8 hours for up to 3 days, then tapered over 4 days. In general, tapering of steroids can start when vasopressors and high-flow oxygen are no longer needed.
 
CRS is considered resolved when there is sustained resolution of fever and there is no longer a need for oxygen supplementation to relieve hypoxia nor vasopressors to maintain blood pressure; however, normalization of temperature alone does not define resolution of CRS.
 |   |

| Event severity (ASTCT CRS Consensus Grading) | Recommended SAR444245 dose modification and supportive care guidelines  | Recommended Cetuximab dose modifications and supportive care guidelines |
|--|---|---|
|  | 
If no clinical improvement in oxygenation, hypotension, fever, and other CRS manifestations is observed within 24 to 72 hours, initiate management for persistent or worsening CRS. Re-evaluation for other contributing conditions will be done, such as infection, cardiac, thromboembolic and other complications. Intravenous Tocilizumab at 8 mg/kg (for participants weighing <math>\geq 30</math> kg) or alternative therapies per site practice in CRS management should be administered, and steroids should be administered concurrently. If still no improvement in oxygenation, hypotension, fever and other manifestations is observed after the first dose of tocilizumab, it may be repeated after an interval of at least 8 hours and should not exceed 4 doses in total.
 
For participants with severe CRS who fail to improve after repetitive treatment with both tocilizumab or alternative therapies per site practice in CRS management and steroids, alternative options will be discussed with clinical site specialists.
 |   |

- a Information for preparation and storage of SAR444245 is provided in the pharmacy manual.
- b Fever is defined as temperature  $\geq 38^{\circ}\text{C}$  not attributable to any other cause. In patients who have CRS then receive antipyretic or anticytokine therapy such as tocilizumab or alternative therapies per site practice in CRS management or steroids, fever is no longer required to grade subsequent CRS severity. In this case, CRS grading is driven by hypotension and/or hypoxia.
- c CRS grade is determined by the more severe event: hypotension or hypoxia not attributable to any other cause. For example, a patient with temperature of  $39.5^{\circ}\text{C}$ , hypotension requiring 1 vasopressor, and hypoxia requiring low-flow nasal cannula is classified as Grade 3 CRS.
- d Low-flow nasal cannula is defined as oxygen delivered at  $\leq 6$  L/minute. Low flow also includes blow-by oxygen delivery, sometimes used in pediatrics. High-flow nasal cannula is defined as oxygen delivered at  $> 6$  L/minute.

Abbreviations: AE = Adverse event; ASTCT = American Society for Transplantation and Cellular Therapy; BiPAP = Bilevel Positive Airway Pressure; CPAP = Continuous Positive Airway Pressure; CRS = cytokine release syndrome; ICU = intensive care unit; IL = Interleukin; IMP = investigational medicinal product; IV = Intravenous; NSAIDs = Non-steroidal anti-inflammatory drugs.

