| Participant is unarousable or requires vigorous or repetitive tactile stimuli to arouse. Stupor or coma.
Life-threatening prolonged seizure (>5 min); or Repetitive clinical or electrical seizures without return to baseline in between. | 
If Grade 4 ICANS, permanently discontinue SAR444245.
 
Treatment with IV corticosteroids should be initiated. Concomitant CRS may require tocilizumab or alternative therapies per site practice in CRS management and should be handled as described in Table 9.
Corticosteroids can then be administered IV or orally every 8 hours for up to 3 days, then tapered over 4 days.
   |
| Deep focal motor weakness such as hemiparesis or paraparesis.   | For both Grade 3 and Grade 4 ICANS  |
| Diffuse cerebral edema on neuroimaging; decerebrate or decorticate posturing; or cranial nerve VI palsy; or papilledema; or Cushing's triad.  | 
If there is no clinical improvement within 24 to 72 hours, then re-evaluation for other contributing conditions should be done. Administration of IV Tocilizumab at 8 mg/kg (for participants weighing ≥30 kg, total dose should not exceed 800 mg) should be considered or alternative therapies per site practice in CRS management, and steroids should be administered concurrently and repeated as previously mentioned for CRS.
 
Neurologist and other relevant clinical specialists should be involved whenever indicated.
 |

a Information for preparation and storage of SAR444245 is provided in the pharmacy manual  
Abbreviations: AE = Adverse event; ASTCT=American Society for Transplantation and Cellular Therapy; CRS= cytokine release syndrome; IV = Intravenous; NCI = National Cancer Institute.

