| Grade 4
ICE score: 0 (participant is unarousable and unable to perform ICE).
Participant is unarousable or requires vigorous or repetitive tactile stimuli to arouse. Stupor or coma.
Life-threatening prolonged seizure (>5 min): or Repetitive clinical or electrical seizures without return to baseline in between.
Deep focal motor weakness such as hemiparesis or paraparesis.
Diffuse cerebral edema on neuroimaging; | If Grade 4 ICANS, permanently discontinue SAR444245.
Treatment with IV corticosteroids should be initiated. Concomitant CRS may require tocilizumab or alternative therapies per site practice in CRS management and should be handled as described in Section 6.5.4.3 . Corticosteroids can then be administered IV or orally every 8 hours for up to 3 days, then tapered over 4 days.

For both Grade 3 and Grade 4 ICANS
If there is no clinical improvement within 24 to 72 hours, then re-evaluation for other contributing conditions should be done. Administration of IV Tocilizumab at 8 mg/kg (for participants weighing ≥30 kg, total dose should not exceed 800 mg) or alternative therapies per site practice in CRS |

| Event severity
(ASTCT Consensus Grading criteria)   | Recommended SAR444245
dose modification and supportive care guidelines   |
|--|---|
| decerebrate or decorticate posturing; or cranial nerve VI palsy; or papilledema; or Cushing's triad. | management should be considered, and steroids should be administered concurrently and repeated as previously mentioned for CRS.

Neurologist and other relevant clinical specialists should be involved whenever indicated. |

a Information for preparation and storage of SAR444245 is provided in the pharmacy manual.

Abbreviations: AE = Adverse event; ASTCT=American Society for Transplantation and Cellular Therapy; CRS= cytokine release syndrome; IV = Intravenous; NCI = National Cancer Institute.

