| Grade 4
ICE score: 0 (participant is unarousable and unable to perform ICE).
Participant is unarousable or requires vigorous or repetitive tactile stimuli to arouse. Stupor or coma.
Life-threatening prolonged seizure (>5 min); or Repetitive clinical or electrical seizures without return to baseline in between.
Deep focal motor weakness such as hemiparesis or paraparesis.
Diffuse cerebral edema on neuroimaging; decerebrate or decorticate posturing; or cranial nerve VI palsy; or papilledema; or Cushing's triad. | If Grade 4 ICANS, permanently discontinue SAR444245.
Treatment with IV corticosteroids should be initiated. Concomitant CRS may require tocilizumab or alternative therapies per site practice in CRS management and should be handled as described in Table 7 .
Corticosteroids can then be administered IV or orally every 8 hours for up to 3 days, then tapered over 4 days.

For both Grade 3 and Grade 4 ICANS
If there is no clinical improvement within 24 to 72 hours, then re-evaluation for other contributing conditions should be done. Administration of IV Tocilizumab at 8 mg/kg (for participants weighing $\geq 30$ kg, total dose should not exceed 800 mg) or alternative therapies per site practice in CRS management should be considered, and steroids should be administered concurrently and repeated as previously mentioned for CRS.
Neurologist and other relevant clinical specialists should be involved whenever indicated. |

a Information for preparation and storage of SAR444245 is provided in the pharmacy manual

Abbreviations: AE = Adverse event; ASTCT=American Society for Transplantation and Cellular Therapy; CRS= cytokine release syndrome; IV = Intravenous; NCI = National Cancer Institute.

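### The CRS and ICANS tables in substudies A2, B1 and B2 give the same tocilizumab dose, but only the ICANS tables state an 800 mg limit, and that limit is not defined

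*Protocol*

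**What the plan says.** **CRS tables** (A2 Table 9, B1 Table 4, B2 Table 7). If CRS does not improve within 24 to 72 hours, intravenous tocilizumab, or an alternative in line with site practice, is to be given "at 8 mg/kg (for participants weighing" at least 30 kg. If there is still no improvement after the first dose, "it may be repeated after an interval of at least 8 hours and should not exceed 4 doses in total". Neither the table cells nor the footnotes state a maximum in milligrams.

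**ICANS tables** (A2 Table 12, B1 Table 6, B2 Table 8), for Grades 3 and 4. In A2 the sentence reads: "Administration of IV Tocilizumab at 8 mg/kg (for participants weighing ≥30 kg, total dose should not exceed 800 mg) should be considered". B1 and B2 carry the same limit (B2: "total dose should not exceed 800 mg) or alternative therapies per site practice in CRS management should be considered"). None of the three says whether it applies to one infusion or to the whole course.

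**The link between them.** A2 Table 12 states: "Concomitant CRS may require tocilizumab or alternative therapies per site practice in CRS management and should be handled as described in" the CRS table. B1 points to its CRS section and B2 to its CRS table. The ICANS sections (A2 6.5.4.6; B1 and B2 6.5.4.5) describe ICANS as frequently accompanying CRS and restrict tocilizumab to the CRS context.

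**The concern.** The two tables govern the same drug at the same weight-based dose, with the same 30 kg threshold, and largely in the same participants. Tocilizumab under the ICANS row presupposes CRS, so overlap is the expected case. A participant with both syndromes falls under one row that states an 800 mg limit and is referred by that table to guidance that states none.

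At stake is the consistency of rescue guidance for Grade 3 and 4 events. Staff who follow the CRS table to the letter could exceed a limit that the protocol states for the same drug elsewhere. Because the limit is undefined, staff who take it as a limit on the whole course could also withhold a repeat dose that the CRS table permits. The pattern recurs in all three substudies, so it is not an isolated typing slip.

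**Working it through.** No sample size, power or error rate is involved, and the plan gives no figure to reproduce. The check is a comparison of wording plus hand arithmetic.

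**Inputs.** Dose 8 mg/kg and threshold 30 kg (both sets of tables); at most 4 doses at least 8 hours apart (CRS tables); 800 mg (ICANS tables). The individual body weights below are illustrative assumptions, because the documents shown give no weight distribution.

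**Side by side.**

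| | CRS tables | ICANS tables |
|---|---|---|
| Dose | 8 mg/kg, at least 30 kg | 8 mg/kg, at least 30 kg |
| Milligram limit | none stated | 800 mg, scope undefined |
| Number of doses | up to 4 | back-reference to CRS; unclear whether it covers tocilizumab or only steroids |

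**Reading 1: 800 mg per infusion.** The tables give the same dose as long as 8 × weight ≤ 800, that is, up to 800 / 8 = 100 kg. Above that they diverge:
- 110 kg: 8 × 110 = 880 mg under CRS, at most 800 mg under ICANS.
- 120 kg: 8 × 120 = 960 mg against 800 mg, a difference of 160 mg.

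**Reading 2: 800 mg for the whole course.**
- Two full doses exceed 800 mg when 2 × 8 × weight > 800, that is, above 800 / 16 = 50 kg.
- Four full doses exceed it when 4 × 8 × weight > 800, that is, above 800 / 32 = 25 kg. This covers everyone in the group of at least 30 kg (30 kg: 4 × 240 = 960 mg).
- 70 kg: one dose 560 mg, two doses 1,120 mg, four doses 2,240 mg.

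**Which reading fits the text better.** Three features favour Reading 1:
- The protocol uses *total dose* elsewhere for the amount prepared for a single infusion from the participant's weight (weight footnote of the schedule of activities and dosage footnote of the IMP overview table, in each substudy). Those footnotes concern study drug, but they show the usage.
- The CRS tables word the course limit differently, as a number of doses.
- In the ICANS row the 800 mg phrase stands in the same parenthesis as the 30 kg threshold, so it qualifies the weight-based dose.

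Reading 2 remains open because no table defines the term.

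**Is there a tie-breaker?** Section 6.5.1 of each substudy says that the most conservative adjustment prevails when recommendations conflict. It stands under dose modification of the study drugs and does not address rescue medication. Nor would it define what 800 mg refers to. Nothing in the text shown reconciles the tables.

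**The case against.** The strongest defence is that a ceiling per infusion and a maximum of four infusions can be obeyed together. On that reading the tables do not contradict each other: the CRS tables omit a limit that the ICANS tables state, and the omission matters only above 100 kg. This is largely right and sets the size of the point. It does not dispose of it, because a participant above 100 kg treated exactly as the CRS table says would receive more than the ICANS table allows, and the ICANS table itself points to the CRS guidance.

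A second defence is that these are recommendations. The ICANS sections say so expressly, tocilizumab for ICANS is only to be considered, alternatives by site practice are allowed, and the final decision lies with the investigator. This lowers the consequence but leaves the mismatch.

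Two stronger readings are tempting, and the documents do not support them:
- A reader might infer that the tables are incompatible for most adults, since two doses pass 800 mg above 50 kg. That rests on the cumulative reading, which the protocol's own usage makes the weaker one. It shows why the term needs defining, not how far the tables conflict.
- A reader might infer a further contradiction from the supply statement in the CRS section: "Sites should have at least 2 full doses of tocilizumab or alternative therapies per site practice in CRS management available". A minimum stock that may be met with alternatives does not conflict with a maximum number of doses. Readiness for severe CRS is also referred to master protocol Section 6.1.4, which is not shown.

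**Conclusion.** The inconsistency is real and present in all three substudies: same drug, same 8 mg/kg, overlapping participants, and a milligram limit in one set of tables only. On the better-supported per-infusion reading its reach is limited to participants above 100 kg (960 mg against 800 mg at an illustrative 120 kg). How many participants that would be cannot be said from the documents. On the cumulative reading, which the undefined wording leaves open, the limit would conflict with the 4-dose allowance, from the second full dose onwards above 50 kg.

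This is an internal inconsistency in recommended rescue guidance, not a matter of design, and it does not touch any endpoint, sample size or analysis. It should still be corrected, because following one table exactly can exceed a limit stated in another for severe or life-threatening events. The conclusion assumes that the master protocol, which is not shown, contains no reconciling statement; the substudy sections cited here refer to it for grading scales and for readiness.

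**What to change.** Reconcile A2 Tables 9 and 12, B1 Tables 4 and 6, and B2 Tables 7 and 8, so that the CRS and ICANS tables carry the same tocilizumab limit wording. State whether 800 mg applies per infusion or to the whole course. Make clear whether the ICANS back-reference on repetition covers tocilizumab or only steroids. The limit itself is for the sponsor to set; this review takes no view on it.

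The cost is wording in six tables. Amendment 03 already revised the tocilizumab wording in the CRS and ICANS sections of B1 and B2, so a further harmonising edit is feasible. No design or analysis element changes.
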